#### **8.6.4 Safety Analyses**

Safety data will be summarized descriptively in aggregate within the safety population. No formal statistical testing is planned for the safety data.

##### **8.6.4.1 Adverse Events**

Adverse events will be summarized and listed by the Medical Dictionary for Regulatory Activities (MedDRA) terms, by preferred term within each system organ class. Summary tables will include all AEs reported from the first radium-223 infusion.

Summaries to be produced include the following:

- Incidence within system organ class (MedDRA).
- Incidence by decreasing frequency.
- Incidence by NCI CTCAE severity grade, by decreasing frequency.
- Incidence of Grade  $\geq 3$  AEs, by decreasing frequency.
- Incidence of SAEs.
- Incidence of AEs within 1 day of infusion.
- Incidence of AEs that resulted in premature discontinuation of study treatments.

Adverse events that occur multiple times for a subject will be counted only once per subject in incidence summary tables. In tables that enumerate AEs by severity, only the greatest severity for an AE occurring multiple times for a subject will be counted.

##### **8.6.4.2 Laboratory Data**

Summaries of laboratory data collected from baseline until study completion will include:

Version 4.0 Date: 08/21/2020

NCT02463799

The values for radium-223 in this protocol has been revised as per the US NIST standardization update (agreed on 17 Mar 2015)

- Incidence of clinically significant laboratory abnormalities by NCI CTCAE v4 [2]. A clinically significant laboratory toxicity is defined as a post-baseline grade 3 or higher toxicity where the baseline value was grade 2 or lower.
- Summary statistics (mean, median, standard deviation, minimum, and maximum) for laboratory values and their change from baseline by time point.

Baseline results will be defined as the most recent nonmissing value obtained on or prior to the randomization date.

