Abbreviations: AE = adverse event; A/P = abdomen/pelvis; CT = computed tomography; ECOG = Eastern Cooperative Oncology Group; F/U = follow up visit; Im = Immune assessment visit; JH = Johns Hopkins; MRI = magnetic resonance imaging; PAP = prostatic acid phosphatase; P/E = physical exam; PET = positron emission tomography; Sip = sipuleucel-T infusion visit; PS = performance status; PreL = preleukapheresis visit; PSA = prostatic specific antigen; Rad = radium-223 infusion visit; SAE = serious adverse event; Tx = treatment

- a. All screening procedures must occur within 28 calendar days prior to registration, with the exception of written informed consent, histological documentation of prostate cancer with Gleason grading, and imaging for confirmation of metastatic disease
- b. Radium-223 visits will occur 6 times at weeks 0, 4, 8, 12, 16, and 20
- c. Applies to all leukapheresis; pre-leukapheresis visits will occur  $\leq 5$  days prior to each leukapheresis. First sipuleucel-T infusion may occur any time between the second and third radium-223 infusion.
- d. At baseline, week 6, 10, 14, 26, 39, and 52 post-first sipuleucel-T infusion
- e. Follow-up visits will occur at every 3 months after week 58 visit for additional 1 year or until the subject's death
- f. Vital signs will be measured 1 to 30 minutes prior to, and at 30 minutes ( $\pm 10$  min) following each infusion
- g. Bone scan and CT or MRI abdomen/pelvis
- h. Per institution's standard procedure/at the investigator's discretion
- i. Only treatment-related events will be collected
- j. Baseline sample can be drawn at subject's "day one visit" (prior to dosing). See Appendix 1 for sample preparation instructions.
- k. Blood samples for antigen spread analysis will be collected at baseline (can be drawn at subject's "day one visit" (prior to dosing) , 1st pre-leukapheresis visit, and weeks 14 and 52 post-first sipuleucel-T infusion.
- l. PTT, PT/INR

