## 6.2 Registration

After eligibility screening, patients who are selected to participate will be registered with the study site/institution. A record of patients who fail to meet entry criteria (ie, screen failures) will be maintained by each individual site. Patient registration must be complete before beginning any treatment or study activities.

Prior to protocol enrollment and initiation of treatment, subjects must sign and date an IRB-approved consent form. To register a patient, the following documents must be completed and faxed or emailed to the Lead Center Program Coordinator:

- Signed patient consent form
- Registration Form
- Copies of the prostate cancer pathology report, baseline laboratory studies including CBC with differential, liver and kidney function tests, testosterone, PSA, and CT/bone scan. Other materials may also be sent if considered pertinent for confirming patient eligibility.

The Lead Center will review the documents to confirm eligibility. To complete the registration process the Lead Center will:

- Assign a patient study number
- Register the patient on the study with SKCCC's Clinical Research Office
- Fax or e-mail the patient study number to the participating site

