## 6.3 Randomization

Eligible subjects will be registered and randomly assigned in a 1:1 ratio to receive 6 infusions of radium-223 and 3 infusions of sipuleucel-T starting after second dose of radium-223 (Arm 1) or 3 infusions of sipuleucel-T alone (Arm 2).

Arm 1: 6 infusions of radium-223 with 3 infusions of sipuleucel-T starting after second dose of radium-223

Arm 2: 3 infusions of sipuleucel-T

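### Laboratory baseline is tied to the randomisation date, so a week-0 value taken before treatment can be tabulated as toxicity, and the same rule omits worsening from grade 3 to grade 4

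*Combined protocol and SAP*

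**What the plan says.** **Baseline.** Section 8.6.4.2 gives one rule for laboratory data: "Baseline results will be defined as the most recent nonmissing value obtained on or prior to the randomization date".

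**What is counted.** The same section states: "A clinically significant laboratory toxicity is defined as a post-baseline grade 3 or higher toxicity where the baseline value was grade 2 or lower". It also plans summary statistics "for laboratory values and their change from baseline by time point".

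**Order of events.**
- Section 6.1, footnote a of both schedules: "All screening procedures must occur within 28 calendar days prior to registration" (with exceptions for consent, histology and imaging, not for blood tests).
- Section 6.3: "Eligible subjects will be registered and randomly assigned in a 1:1 ratio".
- Section 6.2: "Patient registration must be complete before beginning any treatment or study activities".
- No section states how long may pass between randomisation and week 0.

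**Week-0 bloods.** Both Section 6.1 tables mark haematology and chemistry at screening and again at week 0: at Rad-1 in Arm 1 and at PreL-1 in Arm 2. Footnote b of the Arm 2 table places the pre-leukapheresis visit no more than 5 days before leukapheresis. The Arm 1 table does not say whether Rad-1 bloods are taken before or after the infusion.

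**The concern.** A safety baseline should be the last observation before exposure. Here the cut-off is an administrative date that can precede exposure by an unstated interval, and a further set of bloods is scheduled in that gap. Two consequences follow.

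1. A pre-treatment value can land on the post-baseline side. If it is newly grade 3 or higher, the incidence table reports it as toxicity in a patient who has had neither radium-223 nor leukapheresis. Change from baseline is also measured from an older value than the latest one available before treatment.
2. The requirement for a baseline grade of 2 or lower removes patients who enter at grade 3 and worsen to grade 4. This matters mainly for analytes with no entry limit. Lymphocytes are the obvious example: they are in Table 2 (Section 6.9), have no limit in Section 4.1.11, and are among the cells that leukapheresis collects (Section 5.2.2).

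At stake is the accuracy of the one planned table that sets graded laboratory values against baseline. Safety of the combination is a secondary objective (Section 2.2.2).

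**Working it through.** The plan gives no figure for this point, so the check is a classification of cases.

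**Step 1. Which week-0 draws are post-baseline?**

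| Week-0 draw | Relative to treatment | Class under 8.6.4.2 |
|---|---|---|
| On the randomisation date, either arm | not needed | meets the on-or-before rule, so it is itself the baseline |
| PreL-1, Arm 2, after the randomisation date | before leukapheresis | post-baseline |
| Rad-1, Arm 1, after the randomisation date, before infusion | before treatment | post-baseline |
| Rad-1, Arm 1, after the randomisation date, after infusion | after treatment | post-baseline, correctly |

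Rows 2 and 3 are the problem.

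**Step 2. Which grade changes does the incidence rule count?** Take baseline grade b and post-baseline grade p, each 0 to 4.
- Current rule, p ≥ 3 and b ≤ 2: 3 baseline grades × 2 post-baseline grades = 6 transitions.
- Alternative rule, p ≥ 3 and p > b: 7 transitions. The one added is 3 to 4.

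**Step 3. What does moving the baseline change?** Take screening grade b, untreated week-0 grade w (drawn after the randomisation date) and worst on-treatment grade t: 5 × 5 × 5 = 125 patterns.
- Current rule flags if b ≤ 2 and max(w, t) ≥ 3.
- With only the baseline moved to week 0, the rule flags if w ≤ 2 and t ≥ 3.
- Flagged now but not after: b ≤ 2 and w of 3 or 4, any t: 3 × 2 × 5 = 30.
- Missed now but flagged after: b of 3 or 4, w ≤ 2, t of 3 or 4: 2 × 3 × 2 = 12.
- Patterns that change class: 30 + 12 = 42 of 125.

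In 18 of the 30 (3 × 2 × 3, with t ≤ 2), the only grade 3 or higher value is the pre-treatment one.

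**Step 4. Both changes together** (flag if t ≥ 3 and t > w).
- Of the 30, the 3 patterns with w = 3 and t = 4 stay flagged, as true worsening: 30 − 3 = 27.
- The 12 gain 2 patterns, with b of 3 or 4, w = 3 and t = 4: 12 + 2 = 14.
- Total changed: 27 + 14 = 41 of 125.

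These are logical patterns, not expected patients. The documents give no frequencies from which a patient count could be derived.

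**Step 5. Does the primary analysis depend on any of this?** Section 8.2 uses 15 per arm, a 3.6-fold ratio, SD 1.4 on the log scale and one-sided 0.05. Power = Φ(ln 3.6 / (1.4 × √(2/15)) − 1.645) = Φ(1.281 / 0.511 − 1.645) ≈ 0.805. The noncentral t version gives 0.788. The stated 80% is reproduced, and no laboratory baseline enters it.

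**The case against.** Anchoring baseline at randomisation is a recognised convention. It fits Section 6.6.1, which collects adverse events from registration, and Sections 6.5.1 and 6.5.2, which treat earlier findings as medical history. Each arm has one week-0 draw, so the rule touches both arms. Change from baseline is shown by time point, so week-0 values stay visible. The incidence table does not attribute cause; relatedness is judged under Section 7.2. Section 8.6.4 plans no formal safety testing. All of this stands, and it limits the impact. It does not make an untreated value a sound post-baseline value. Nor does the plan hold to randomisation throughout: the safety population (Section 8.3) starts from the first leukapheresis or radium-223 dose, and the adverse event tables (Section 8.6.4.1) from the first radium-223 infusion.

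A reader might infer more than the documents support:

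- **That week-0 bloods in general count as toxicity.** Only a week-0 value of grade 3 or higher, with a baseline grade of 2 or lower, drawn after the randomisation date, is affected. For Arm 1 the draw must also precede the infusion, which is not stated.
- **That worsening from grade 3 to 4 is lost altogether.** It is omitted from the Section 8.6.4.2 incidence count. It can still appear in the maximum-grade endpoint (Section 8.5.2), in the change and range summaries, and in the adverse event tables if it meets Section 7.6. These routes are partial. Maximum grade has no baseline comparison, and Section 7.6 keeps other laboratory abnormalities off the adverse event form.
- **That a share of draws measures the problem.** Counting haematology draws after screening gives 1 of 12 in Arm 1. In Arm 2 it gives 1 of 9 from the Section 3.0 visit list, or 1 of 3 from the Section 6.1 table. The table counts units of blood drawing, whereas incidence concerns patients. The 1 of 3 rests on a separate mismatch between Section 3.0 and the Arm 2 table.
- **That the immune-assay baseline conflicts with this rule.** The Section 6.1 footnote, "Baseline sample can be drawn at subject's 'day one visit' (prior to dosing"), is a permission about collecting samples for other assays. Section 8.6.4.2 governs laboratory data, so the two do not contradict each other.

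**Conclusion.** The point holds and is minor. As written, the rule can class a pre-treatment value as post-baseline, and its incidence definition leaves out exactly one kind of worsening to grade 3 or higher, namely grade 3 to grade 4.

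It rests on these assumptions:
- At least some week-0 draws fall after the randomisation date. The order of registration and treatment makes this plausible, but no interval is given.
- For Arm 1, Rad-1 bloods are taken before the infusion.
- For the grade 3 to 4 part, patients can enter at grade 3. Section 4.1.11 limits neutrophils, platelets, haemoglobin, bilirubin, AST, ALT, creatinine and albumin. If those limits lie below grade 3 (the grading cut-offs are not in the documents), this part concerns mainly ungated analytes such as lymphocytes, sodium, potassium, phosphorus and glucose. A new grade 3 value at week 0 is also less likely for the gated analytes.

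The number of patients affected cannot be estimated from the documents. Safety is descriptive, and the primary comparison, sample size and power are untouched. The change is still worth making, because the better rule is specific and nearly free.

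**What to change.** Replace two sentences in Section 8.6.4.2:

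- *Laboratory baseline is the last non-missing value obtained before the first radium-223 infusion in Arm 1 or before the first leukapheresis in Arm 2.*
- *A clinically significant laboratory toxicity is a post-baseline value of grade 3 or higher whose grade exceeds the baseline grade.*

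The change is confined to laboratory data; the immune-assay baseline can stay as it is.

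The cost is these two sentences and the matching table code, with no extra blood draws. The one practical task is to confirm from source records that Rad-1 bloods in Arm 1 preceded the infusion. Where that cannot be shown, use the latest value known to precede it, normally the screening value, and report how many patients this affects.

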#### **8.6.4.3 Vital Signs**

Vital sign data (blood pressure, respiration rate, heart rate, and body temperature) will be summarized descriptively by time point.

#### **8.6.5 Study Treatment Administration**

Leukapheresis and sipuleucel-T infusion information will be summarized.

This will include the following:

- Number of subjects who received a total of 0, 1, 2, or 3 infusions.
- Reason(s) for not completing 3 infusions.
- Number of subjects who receive a total of 0, 1, 2, 3, 4, or 5 or more leukaphereses.
- Number of subjects who receive a total of 3 leukaphereses and 3 infusions of sipuleucel-T

The duration of treatment with radium-223 will be summarized.

This will include the following:

- Number of subjects who received a total of 0, 1, 2, 3, 4, 5, or 6 infusions.
- Reason(s) for not completing 6 infusions.

#### **8.6.6 Concomitant Medications and Procedures**

Concomitant medications and procedures will be presented in data listings and will be coded using the World Health Organization Drug Dictionary. Separate summaries will be provided for medications that were started prior to registration and for medications started after registration.

#### **8.7 Interim Analyses**

Version 4.0 Date: 08/21/2020

NCT02463799

The values for radium-223 in this protocol has been revised as per the US NIST standardization update (agreed on 17 Mar 2015)

We will carry out interim safety assessments with statistical monitoring. We will monitor patients in groups of 10 (5 per treatment arm). The formal monitoring rule relates to the risk of hematologic adverse events. Specifically, we will monitor thrombocytopenia, neutropenia, and anemia.

- >2 events of grade  $\geq 3$  thrombocytopenia or neutropenia in the first 10 subjects
- >3 events of grade  $\geq 3$  anemia in the first 10 subjects

## **9.0 REGULATORY REQUIREMENTS**

### **9.1 Investigator Responsibilities**

The Principal Investigator is responsible for performing the following tasks:

- Coordinating, developing, writing, submitting, and obtaining IRB-approval for the protocol as well as its subsequent amendments.
- Assuring that all study personnel are using the correct version of the protocol.
- Taking responsibility for the overall conduct of the study and for monitoring the progress of the study.
- Reviewing and ensuring reporting of serious adverse events (SAEs).
- Reviewing data from all patients.

### **9.2. Study Coordinator Responsibilities**

The study coordinator is responsible for performing the following tasks:

- Ensuring that IRB approval has been obtained prior to patient registration, and maintaining copies of IRB approvals (including approval of amendments).
- Managing patient registration.
- Collecting and compiling data from each patient.
- Establishing procedures for documentation, reporting, and submission of AEs/ SAEs to the principal investigator ([name]) and other applicable parties.
- Data entry and query answering.
- Facilitating audits by securing selected source documents and research records from participating patients for audit.

### **9.3 Study Personnel Responsibilities**

Study personnel (co-investigators, research nurses) are responsible for these tasks:

- Following the protocol as written, and Good Clinical Practice (GCP) guidelines.

Version 4.0 Date: 08/21/2020

NCT02463799

The values for radium-223 in this protocol has been revised as per the US NIST standardization update (agreed on 17 Mar 2015)

- Submitting data to the project manager.
- Registering all patients by submitting the patient registration form and signed informed consent form promptly.
- Providing sufficient experienced clinical and administrative staff and adequate facilities and equipment to conduct the trial according to the protocol.
- Maintaining regulatory binders and providing copies of all required documents to the project manager.
- Collecting/submitting data according to the schedule specified by the protocol.

#### **9.4 Participating Sites Responsibilities**

Participating sites are responsible for performing the following tasks:

- Following the protocol as written, and the guidelines of GCP.
- Submitting data to the Lead Center (SKCCC)
- Registering all patients with the Lead Center (SKCCC) by submitting patient registration form, and signed informed consent promptly
- Providing sufficient experienced clinical and administrative staff and adequate facilities and equipment to conduct a collaborative trial according to the protocol
- Maintaining regulatory binders on site and providing copies of all required documents to the Lead Center (SKCCC)
- Collecting and submitting data according to the schedule specified by the protocol
- Query resolving

#### **9.5 Patient Information and Informed Consent**

Before obtaining consent, members of the study team will review the rationale for the treatment program with the patient. The discussion will review the alternatives available (including hormonal therapy, chemotherapy, or supportive care as appropriate), the potential benefits of this program, the risks and the probability of their occurrence, and the procedures to minimize these risks. Should an adverse event occur, the provisions available to ensure medical intervention will also be reviewed. Why the risks are reasonable in relation to the anticipated benefits, incentives, or costs that will or may be incurred as a result of participating in the study, as well as the efforts to maintain confidentiality, will also be discussed with the patient.

Patients will be required to sign and date (in triplicate) a statement of informed consent that meets the requirements of the Code of Federal Regulations (Federal Register Vol. 46, No. 17, January 27, 1981, part 50) and the IRB. The medical record will include a statement that written informed consent was obtained (and document the date that it was obtained) before the patient is enrolled in the study. The original signed document will become part of the patient's medical record and a copy will be sent home with each patient.

The consent form will include the following:

Version 4.0 Date: 08/21/2020

NCT02463799

The values for radium-223 in this protocol has been revised as per the US NIST standardization update (agreed on 17 Mar 2015)

- the nature and objectives, potential toxicities, and benefits of the intended study
- the length of therapy and likely follow-up required
- alternatives to the proposed therapy (standard and investigational therapies)
- the name of the investigator(s) responsible for the protocol
- the right of the patient to accept or refuse treatment and to withdraw from the study

Subjects who are on-treatment at the time the new NIST reference standard goes into effect should be notified of this change and should be required to sign a Patient Information Sheet to acknowledge that they have received information on the updated NIST standard calibration. All patients randomized after the new reference standard is in effect should sign a revised Informed Consent Form that contains the updated NIST standardization.

## **9.6 Subject Confidentiality**

Patients will be informed of the extent to which their confidential health information generated from this study may be used for research purposes. After this discussion, they will be asked to sign a Notice of Privacy Practice research authorization/HIPAA form. The original signed documents will become part of the patient's medical records, and each patient will receive a copy of the signed documents. The use and disclosure of protected health information will be limited to the individuals described in the research authorization form. The research authorization form must be completed by the Principal Investigator and approved by the IRB.

## **9.7 Good Clinical Practice**

The study will be conducted in accordance with the ICH for GCP and the appropriate regulatory requirement(s). The investigator will be thoroughly familiar with the appropriate use of the study drug as described in the protocol and Investigator's Brochure. Essential clinical documents will be maintained to demonstrate the validity of the study and the integrity of the data collected. Master files should be established at the beginning of the study, maintained for the duration of the study and retained according to appropriate regulations.

## **9.8 Ethical Considerations**

This study will be conducted in compliance with the protocol, GCP guidelines established by the International Conference on Harmonization, and the ethical standards set forth in the Declaration of Helsinki 2004 (available at: [www.laakariliitto.fi/e/ethics/helsinki.html](http://www.laakariliitto.fi/e/ethics/helsinki.html)).

## **10.0 STUDY MANAGEMENT**

### **10.1 Clinical Trial Agreement**

Version 4.0 Date: 08/21/2020

NCT02463799

The values for radium-223 in this protocol has been revised as per the US NIST standardization update (agreed on 17 Mar 2015)

This trial is being conducted under one or more clinical trial agreements that contain, among other terms, the publication policy, indemnity agreements, and financial arrangements for the study.

